3.5 STUDY SIZE

The primary objective of this NIS is to assess the treatment patterns of BRAF^{V600E} mutant mCRC patients. The sample size was determined based on the precision with which the primary objective could be achieved. Precision estimates were calculated around percentages ranging from 1% to 20% for sample sizes ranging from 200 to 1000 (Table 5). The range of proportions was determined based on projected estimates of patient share as per different regimens in first-line therapy in the UK, Germany, France, Spain, and Italy using Oncology Dynamics data which projected proportions of different lines of therapy between 1% to 21%.

Table 5 Precision estimates for a range of proportions and cohort sizes

Proportion	Sample size								
	200	300	400	500	600	700	800	900	1000
1%	±1.38%	±1.13%	±0.98%	±0.87%	±0.80%	±0.74%	±0.69%	±0.65%	±0.62%
5%	±3.02%	±2.47%	±2.14%	±1.91%	±1.74%	±1.61%	±1.51%	±1.42%	±1.35%
10%	±4.16%	±3.39%	±2.94%	±2.63%	±2.40%	±2.22%	±2.08%	±1.96%	±1.86%
15%	±4.95%	±4.04%	±3.50%	±3.13%	±2.86%	±2.64%	±2.47%	±2.33%	±2.21%
20%	±5.54%	±4.53%	±3.92%	±3.51%	±3.20%	±2.96%	±2.77%	±2.61%	±2.48%

A sample size of 300 patients will be able to measure treatment regimens prescribed to 5%, 10%, and 20% patients with a precision of ± 2.5%, ± 3.4%, and ± 4.5%, respectively. This was considered adequate to meet the descriptive objectives of this study.

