This retrospective, multi-center longitudinal study on BRAF^{V600E} mutant mCRC patients will be conducted in Europe to characterize the first-line treatment patterns. All BRAF^{V600E} mutant patients having initiated a first-line treatment for mCRC between January 1st, 2016 and December 31st, 2018 (both days inclusive) with drugs registered for mCRC in respective country will be eligible to participate. Thus the observation period is earlier than the date of inclusion of the patient in the study. The study will not provide or recommend any treatment or procedure; all decisions regarding treatment are made at the sole discretion of the treating physician in accordance with their usual practices and all eligible patients will be considered for enrollment.

The target countries for patient enrollment will include Germany, France, Italy, UK, Spain, Belgium, Austria and the Netherlands. Approximately 300 adult patients (≥ 18 years) from a mix of academic and non-academic sites (up to 65 sites) will be enrolled.

In order to obtain a representative sample of real-world patients undergoing treatment for BRAF^{V600E} mutant mCRC, an evidence-based approach will be adapted to (1) find and select sites within a country that meet the right criteria for success and representability (taking into account various site-level factors such as center type [public/private, academic/non-academic], center size, center practice, etc.), and (2) identify and mitigate risks that could impact patient enrollment. A strategy plan for site selection will be created before site enrolment to ensure site representativeness, and will describe all processes related to the representativity survey. The site survey will be conducted prior site selection.

Patient data will be collected from the date of the start of first-line treatment for mCRC until the end of the observation period (date of death or last day of study observation period for patients alive at the time of data abstraction). Patients lost to follow-up will be censored at the date of their last available medical record.

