The primary objective of this NIS is to assess the treatment patterns of BRAF^{V600E} mutant mCRC patients. The sample size was determined based on the precision with which the primary objective could be achieved. Precision estimates (95% [CIs) were calculated around percentages ranging from 1% to 20% for sample sizes ranging from 200 to 1000. The range of proportions was determined based on projected estimates of patient share as per different regimens in first-line of therapy in UK, Germany, France, Spain, and Italy using Oncology Dynamics data which projected proportions of different lines of therapy between 1% to 21%. A sample size of 300 patients will be able to measure treatment regimens prescribed to 5%, 10%, and 20% patients with a precision of $\pm 2.5\%$ (95% CI: 2.5% to 7.5%), $\pm 3.4\%$ (95% CI: 6.6% to 13.4%) and $\pm 4.5\%$ (95% CI: 15.5% to 24.5%), respectively. This was considered adequate to meet the descriptive objectives of this study. Further details are provided in section 3.5.

Statistical analyses

Statistical analyses will be fully described in a written SAP. The study endpoints will be analyzed overall, by country and by predefined subgroup(s) of interest (e.g., age, gender, primary tumor location, number of metastatic organs). Analyses will be descriptive in nature, as no hypothesis will be tested. In general, missing data will not be imputed (except for dates) and the data will be analyzed according to the complete case approach.

The treatment patterns of patients, baseline demographic and clinical characteristics, time to BRAF mutation testing and description of testing procedures, and reasons for treatment discontinuation will be described using summary statistics. Categorical variables will be summarized by frequencies and percentages. Continuous variables will be summarized by descriptive statistics (mean, and standard deviation, median, 25th and 75th percentiles, minimum and maximum). The number of missing observations for each variable will also be reported. Relevant AEs will be coded by MedDRA and summarized as SOC and PT.

Time-to-event data (PFS, OS, time to treatment cessation) will be evaluated using Kaplan-Meier survival curves. Median survival estimates will be reported along with the 25th and 75th percentiles, and corresponding 95% CIs. Cox regression analysis may be performed to adjust for predefined (baseline) covariates.

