The treatment combination resulted in a median overall survival of 9.0 months (95% confidence interval [CI] = 8.0–11.4 months) in patients treated with the triplet compared to 5.4 months (95% CI = 4.8–6.6 months) for the control regimens (hazard ratio = 0.52, 95% CI = 0.39–0.70; $P < .0001$). The objective response rate for the targeted triplet therapy was 26%, compared to 2% for the controls. The triplet combination was generally well tolerated with no unexpected toxicities. Grade 3 or higher adverse events were seen in 58% of patients on triplet treatment, 50% of those in the doublet group, and 61% of those in the standard therapy group.

50

Data from the BEACON CRC trial are being used to support regulatory approval of the triplet combination in BRAF V600E–mutant metastatic colorectal cancer, and BRAF inhibitor–based treatment has recently been included as a treatment option in the National Comprehensive Cancer Network© (NCCN©) Guidelines for colon and rectal cancers in the United States.

In light of the early clinical data of the Phase III BEACON CRC study, a Phase II, open label, single-arm, multi-center study, the ANCHOR CRC study, is currently ongoing to evaluate the antitumor activity of the Triplet combination of encorafenib, binimatinib and cetuximab by assessing the confirmed ORR in adult subjects with previously untreated BRAF^{V600E} mutant mCRC, where a total of 90 subjects will be enrolled and the study treatment will be administered in 28-day cycles until disease progression, unacceptable toxicity, withdrawal of consent, initiation of subsequent anticancer therapy or death. After discontinuation of the study treatment, subjects will be followed for survival until 1 year after the start of the treatment of the last subject enrolled.

STUDY RATIONALE

The presence of a BRAF^{V600E} mutation is considered a marker of poor prognosis in patients with mCRC, and findings from clinical trials have largely remained inconclusive regarding the efficacy of first-line treatment options for BRAF^{V600E} mutant mCRC patients. In the absence of a targeted/specific treatment for BRAF^{V600E} mutant mCRC, treatment practices can vary based on local practices and guidelines. There is, therefore, an unmet need to document the current practices for first-line treatment of BRAF^{V600E} mutant mCRC, and their effectiveness and safety in a real-world setting.

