3.2.3.2 Participant data collection

Patients data will be collected from the start of first-line treatment for mCRC until the end of the observation period (date of death or last day of study observation period, ie. January 31st, 2020). Patients lost to follow-up will be censored at the date of their last available medical record or the date when they were last known to be alive. The data will be anonymized during the entry into the eCRF by using an algorithm which generates a random patient number without any indication of the patient, centre or country. This anonymization will be maintained in the database used for statistical analysis.

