3.8.2 Primary analyses

The first-line treatment patterns of patients, including the regimen received, duration of treatment, maintenance therapy (if any), and concomitant medications/therapies received, will be summarized using descriptive statistics. Ninety-five percent CIs will be calculated for point estimates, but no statistical adjustments will be made for multiple comparisons.

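### The stated precision assumes 300 independent patients although they come from up to 65 sites, and the anonymisation text appears to rule out allowing for site in the analysis

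*Combined protocol and SAP*

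**What the plan says.** **Sample.** The synopsis (Study design) states: "Approximately 300 adult patients (≥ 18 years) from a mix of academic and non-academic sites (up to 65 sites) will be enrolled". Under section 3.2.3.1 each site works through its list until a per-site target is met or the list is exhausted. The target is not given.

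**Precision.** The synopsis (Sample size) explains: "Precision estimates (95% [CIs) were calculated around percentages ranging from 1% to 20% for sample sizes ranging from 200 to 1000". Section 3.5 puts the figures at ±2.5%, ±3.4% and ±4.5%, in the sentence that begins: "A sample size of 300 patients will be able to measure treatment regimens prescribed to 5%, 10%, and 20% patients with a precision of". Neither place mentions sites, an ICC or a design effect.

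**Local practice.** The study rationale in section 1 says that "treatment practices can vary based on local practices and guidelines". Section 3.1 has sites selected with regard to type, size and practice.

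**Analysis.** Section 3.8.2 says "Ninety-five percent CIs will be calculated for point estimates" and names no method. Nothing in section 3.8 mentions clustering. Section 3.8.1 leaves detailed methods to an SAP whose text is not in the document reviewed.

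**Identifiers.** Section 3.2.3.2 gives each patient "a random patient number without any indication of the patient, centre or country" and carries this through to the analysis database. Section 3.7 has the site-held enrolment record destroyed at database lock. Section 3.8.1 nevertheless plans to analyse the endpoints by country.

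**The concern.** The primary endpoint is which regimen a patient received. Patients at one centre share prescribers, local guidelines and tumour boards, so their regimens may well resemble each other more than those of patients elsewhere. The rationale itself gives variation in local practice as a reason for the study. Assuming no correlation within site sits uneasily with that.

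Two things are at stake. First, the precision offered as the justification for 300 patients may not be delivered, and 95% intervals that ignore site would then cover the true share less often than stated. The results are meant to put a single-arm trial in context and may support health technology assessment, so readers will rely on the stated uncertainty. Second, if the analysis database holds no site field, the omission cannot be repaired after lock, and variation between sites in the primary endpoint could be neither allowed for nor described.

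**Working it through.** **Inputs from the documents.** 300 patients and at most 65 sites (synopsis, Study design); two-sided 95% intervals (synopsis, Sample size); shares of 5%, 10% and 20% (section 3.5).

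**Assumptions.** The ICC and the coefficient of variation (CV) of site size are not in the documents, so ranges are shown.

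**Step 1: reproduce the plan's figures.** Half-width = 1.96 × √(p(1−p)/n).
- p = 0.05: 1.96 × √(0.0475/300) = 2.47%
- p = 0.10: 1.96 × √(0.09/300) = 3.39%
- p = 0.20: 1.96 × √(0.16/300) = 4.53%

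These match Table 5. All 45 cells of the table agree with this formula to within 0.006 percentage points, so the stated precision does assume independent patients.

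**Step 2: design effect with equal sites.** Mean site size m = 300/65 = 4.62. Because 65 is a maximum, this is the smallest possible mean for 300 patients. DEFF = 1 + (m−1) × ICC = 1 + 3.62 × ICC. Each half-width is multiplied by √DEFF, and the effective sample size is 300/DEFF.

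| ICC (assumed) | DEFF | √DEFF | Effective n | 5% share | 10% share | 20% share |
|---|---|---|---|---|---|---|
| 0 (Table 5) | 1.00 | 1.00 | 300 | ±2.47% | ±3.39% | ±4.53% |
| 0.02 | 1.07 | 1.04 | 280 | ±2.55% | ±3.52% | ±4.69% |
| 0.05 | 1.18 | 1.09 | 254 | ±2.68% | ±3.69% | ±4.92% |
| 0.10 | 1.36 | 1.17 | 220 | ±2.88% | ±3.96% | ±5.28% |
| 0.20 | 1.72 | 1.31 | 174 | ±3.24% | ±4.46% | ±5.94% |

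**Step 3: unequal or fewer sites.** With unequal sites, DEFF = 1 + ((1+CV²)m − 1) × ICC.
- 65 sites, CV 0.6: ICC 0.05 gives DEFF 1.26 and ±5.09% at a 20% share; ICC 0.10 gives 1.53 and ±5.59%.
- 30 equal sites (m = 10), ICC 0.10: DEFF = 1 + 9 × 0.10 = 1.90 and ±6.24% at a 20% share.

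**Step 4: coverage of nominal 95% intervals that ignore site.** Beta-binomial simulation at a 10% share, with 40 sites of 5 patients and 25 of 4 (300 in all), 20,000 runs.

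| ICC | Wald | Clopper-Pearson |
|---|---|---|
| 0 | 93.6% | 96.6% |
| 0.02 | 92.7% | 95.9% |
| 0.05 | 91.4% | 95.0% |
| 0.10 | 89.1% | 93.0% |
| 0.20 | 84.2% | 89.0% |

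Part of the Wald shortfall is present without any clustering. The rest comes from ignoring site.

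**Step 5: the identifier passages side by side.**
- The synopsis and section 3.2.3.2 remove centre and country from the patient number and keep it so for analysis. Section 3.8.1 plans by-country results, which need a country field. Section 4.4 adds that reports will not identify countries.
- Section 3.6 has data pseudonymised on entry and anonymised at lock. Section 3.7 has them anonymised on entry.
- Section 3.7 lets each site see its own patients, so the data capture system must hold a site link while the study runs.

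**The case against.** The strongest reply is that the effect may be minor. The rationale says practice can vary locally. It does not say that it varies by site, and guideline differences may be national, which a by-country analysis would partly describe. With about 4.6 patients per site, an ICC of 0.02 widens the intervals by about 4% and one of 0.05 by about 9%. In a descriptive study with no hypothesis test, that would hardly change a reading. All of this stands, and it limits the size of the point.

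A reader might infer that every regimen-share interval will be too narrow. The documents do not show this. Section 3.8.2 names no method. The one interval that the protocol does name for a proportion is Clopper-Pearson, for adverse events in section 3.8.3. If that were used for regimen shares, coverage would still be about 95% at a 10% share with ICC 0.05 and 65 near-equal sites. It would, however, fall to 93.0% and 89.0% at ICC 0.10 and 0.20.

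A reader might also infer that no site variable will exist. A patient number without a centre code does not prove that. The wording points that way, but the by-country analysis implies some location field. What can be shown is the conflict.

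Finally, removing the centre is a deliberate privacy measure. Sections 3.7 and 4.3 promise patients that their data will be used in fully anonymised form. That is a real constraint on the remedy, though a non-identifying code may be compatible with it.

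**Conclusion.** The point holds in conditional form. The stated ±2.5%, ±3.4% and ±4.5% assume independence, and any positive within-site correlation makes them optimistic. Intervals that ignore site are then likely to under-cover. The size rests on an ICC that the documents do not give: at a 20% share the half-width is about 4.7% to 5.9% over assumed ICCs of 0.02 to 0.20 with 65 equal sites. It is small below about 0.05 and material from about 0.10, or with fewer or unequal sites. The consequence is confined to interval width and coverage, since no hypothesis is tested.

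Separately, and without any assumption, the anonymisation passages and the by-country analysis cannot both stand as written. Read literally, the former also exclude a site-clustered analysis.

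One might go further and say that a regimen favoured by a few sites would pass for a European pattern. That is a question of which sites are selected, which the protocol addresses through its site survey and selection plan. Allowing for clustering leaves the point estimates where they are if patients stay equally weighted.

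**What to change.** 1. Reconcile the synopsis and sections 3.2.3.2, 3.6, 3.7 and 4.4 with the by-country analysis in section 3.8.1: say when anonymisation happens and which location fields survive it.
2. Before database lock, keep a country field and one arbitrary, non-identifying code per site in the analysis database, with the key destroyed along with the enrolment record. Check small sites for re-identification risk first.
3. Specify in section 3.8.2 and the SAP that regimen-share intervals treat site as the cluster (survey-type or GEE robust variance), and name the interval method. Use site-clustered standard errors in any Cox or logistic model.
4. State in section 3.5 and the synopsis that Table 5 assumes independent patients, and add a design-effect range such as the one above.

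**Cost.** No extra patients are needed. The price is a somewhat less favourable stated precision, SAP wording, one added code and the re-identification check. The sponsor should also check whether the patient information still describes the data accurately, and whether the change is substantial enough to need ethics submission under section 4.2. The code must be settled before lock, because the site-held link is destroyed then.

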3.6 Personal data mapping

With regards to the EU Reg n°2016/679 on protection of personal data :

- all collected data are entered pseudonymously into the eCRF and will be anonymized during the database lock.
- the storage place during the study is predefined as follow: electronic data capture (EDC) of the CLINFILE company, servers located in France at the HDS-certified hosting provider, Cegedim.
- the data will be stored during the whole study duration in EDC. At the end of the study, CLINFILE will transfer the anonymized database onto a media support (CD/DVD) and then delete the database from Cegedim's servers. The sponsor will archived the media support during 10 years after the database transfer.

3.7 DATA MANAGEMENT

All medical data will be confidential. According to the European Union General Data Protection Regulation 2016/679, sponsoring pharmaceutical company acting as data controller will ensure information of the patients about the use of their health data in completely anonymized form. He will also inform the patient that the local care team will keep an identification record of their data entry for a short period of time only and that it will not be possible to exercise their rights laid down in the GDPR (notably article 15-20) after anonymization by destruction of this record.

All data will be collected and entered directly into the EDC system in an anonymized way. All participating sites will have access to the data entered regarding the individual site's own enrolled patients. All sites will be fully trained on using the on-line EDC, including eCRF completion guidelines and help files. Sites will be responsible for entering extracted patient data into a secure online EDC database via the eCRF. Investigators and data entry staff will be able to access their account with a username and password. All eCRFs should be completed by designated, trained personnel or by the study coordinator, as appropriate. In all cases, the eCRF should be reviewed, electronically signed and dated by the Principal Investigator. All changes or corrections to eCRFs will be documented in an audit trail and an adequate explanation for such changes or corrections will be required. The data will be anonymized during the entry into the eCRF by using an algorithm which generates a random patient number without any indication of the patient, centre or country. In order to ensure data quality, an enrollment record will be maintained at the site until the eCRFs have been remotely monitored and validated. Upon database lock, the enrollement record will be destroyed by the care team, rendering the data completely anonymous.

A data management plan, aligned with the study design, will be created before the start of data collection and will describe all functions, processes, and specifications for data collection, cleaning and validation to ensure that the data are as clean and accurate as possible when presented for analysis.

3.8 DATA ANALYSIS

3.8.1 General considerations

All computations and generation of tables, listings and data for figures will be performed using SAS® version 9.2 or higher (SAS Institute, Cary, NC, USA). Statistical analyses will be fully described in a written Statistical Analysis Plan (SAP), which will be prepared before database lock. The SAP will detail the most appropriate statistical methodology and analyses to be performed in accordance with the study design and objectives.

The Full Analysis Set (FAS) containing all patients who fulfil the eligibility criteria, will be used for this study. If a patient withdraws consent, the patient's data collected before the consent withdrawal will remain in the dataset. Patients in the FAS will also be included in the safety analysis set.

The study endpoints will be analyzed overall, by country and by pre-defined subgroup(s) of interest (e.g., age, gender, primary tumor location, number of metastatic organs). Further details will be provided in the SAP.

Analyses will be descriptive in nature, as no hypothesis will be tested. Data will be analyzed according to the complete case approach, where patients with missing data for relevant variable(s) will be excluded.

Categorical variables will be summarized by frequencies and percentages. Continuous variables will be summarized by descriptive statistics (mean, and standard deviation, median, 25th and 75th percentiles, minimum and maximum). The number of missing observations for each variable will also be reported.

3.8.2 Primary analyses

The first-line treatment patterns of patients, including the regimen received, duration of treatment, maintenance therapy (if any), and concomitant medications/therapies received, will be summarized using descriptive statistics. Ninety-five percent CIs will be calculated for point estimates, but no statistical adjustments will be made for multiple comparisons.

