3.3 STUDY OUTCOMES

3.3.1 Primary endpoint

The primary endpoints are first-line SACT treatment patterns in BRAF^{V600E} mutant mCRC patients, described by:

- Agent or combination of agents received
- Duration of treatment
- Maintenance therapy (if any)

The first-line SACT regimen(s) will be described from the time of treatment initiation (for mCRC) until the time of first documented disease progression, treatment discontinuation or switch, whichever is earlier.

LOT definition will be connected to treatment progression. The LOT will be defined using a data-driven approach. In the SAP an algorithm for LOT definition will be specified, which will consider the specific treatment(s) received (stop and start dates), progression (as recorded in the patient medical record, including date), documented reasons for discontinuation of treatments and gap(s) between subsequent treatment regimens.

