3.8.3 Secondary analyses

- **Demographic and clinical profile**

Demographics and baseline clinical characteristics of patients (as outlined in Table 3) will be summarized using descriptive statistics.

- **Progression free survival**

Progression free survival is defined in Table 2. This will be assessed for first-line treatments and described graphically by Kaplan-Meier (KM) survival curves. Median PFS, 25th and 75th percentiles, and corresponding 95% CI will be reported. Cox regression analysis may be performed to adjust for predefined (baseline) covariates and HR and 95% CIs reported.

- **Overall survival**

Overall survival is defined in Table 2. This will be described graphically by KM survival curves and median OS, 25th and 75th percentiles, and correspondent 95% CI reported. Cox regression analysis may be performed to adjust for predefined (baseline) covariates; HRs and 95% CIs will be reported.

- **Treatment response**

The category of objective response following treatment (CR, PR, and PD) will be summarized by first-line SACT treatments (monotherapy, doublet therapy, triplet therapy) and by treatment regimens using frequency tables with their associated 95% CIs. Additionally, ORR is defined in Table 2. Logistic regression may be used to adjust for predefined (baseline) covariates; odds ratios with 95% CIs will be reported.

- **Treatment duration (time to treatment cessation)**

Time to treatment cessation (defined in Table 2) will be assessed for first-line SACT treatments. This will be described graphically by KM survival curves. Cox regression may be used to adjust for predefined (baseline) covariates; HRs and 95% CIs will be reported.

- **BRAF Mutation testing**

Time from metastatic diagnosis to BRAF mutation testing will be assessed in addition to the time from testing to first-line treatment, and all testing procedures will be summarized using descriptive statistics.

- **Safety analyses**

The number and percentage of patients who have at least one of the relevant AE during first-line treatment will be summarized. Clopper-Pearson (Exact) 95% CIs for the proportion will be constructed around the point estimate of the incidence. Tables with counts and frequencies of relevant AEs will be provided and summarized by MedDRA SOC and PT.

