3.8.4 Exploratory analyses

- **Reason(s) for treatment alteration**

The reasons for treatment alteration (dose change, interruptions, switches, discontinuation), as recorded in patient medical records, will be described using descriptive statistics.

- **Treatment patterns for second (and subsequent) LOT**

Second- (and subsequent-) line treatment patterns, in the subset of patients who progress beyond first-line treatment, will be analyzed based on the methods described in primary analysis (Section 3.8.2).

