3.8.5 Missing data

Due to the nature of the study, missing data (i.e., data that are not collected or documented in the patient's medical record or EMR) may be observed for some variables. In general, missing data will not be imputed (except for dates) and the data will be analyzed according to complete case approach. Partial dates will be imputed using the rules described in the SAP.

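### Duration of treatment, a component of the primary endpoint, is summarised without censoring in 3.8.2 and 3.8.4, although a censored Kaplan-Meier analysis of nearly the same first-line interval is already planned

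*Combined protocol and SAP*

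**What the plan says.** Section 3.3.1 makes duration of treatment one of three descriptors of the primary endpoint and follows the first-line regimen "until the time of first documented disease progression, treatment discontinuation or switch, whichever is earlier". Table 1 measures duration by a start date and a stop date.

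The primary analysis (3.8.2) states that first-line patterns, "including the regimen received, duration of treatment, maintenance therapy (if any), and concomitant medications/therapies received, will be summarized using descriptive statistics". Section 3.8.1 defines the summary: "Continuous variables will be summarized by descriptive statistics (mean, and standard deviation, median, 25th and 75th percentiles, minimum and maximum". The same section adds: "Data will be analyzed according to the complete case approach, where patients with missing data for relevant variable(s) will be excluded". Section 3.8.5 exempts dates from the no-imputation rule, but the rules it points to are for partial dates and are left to the SAP.

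For second and later lines, 3.8.4 says that patterns "will be analyzed based on the methods described in primary analysis".

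The secondary analysis in 3.8.3 reads: "Time to treatment cessation (defined in Table 2) will be assessed for first-line SACT treatments. This will be described graphically by KM survival curves". Table 2 runs that endpoint from first-line initiation to progression, discontinuation or switch. Patients with none of these are censored at the earliest of last record, end of observation or death. The synopsis (Statistical analyses) lists time to treatment cessation among the Kaplan-Meier endpoints and promises the median, quartiles and 95% CIs.

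**The concern.** Time on treatment is a time-to-event quantity. Some patients will have had no progression, discontinuation or switch by 31 January 2020, or by their last record. A mean, SD and quartiles need a completed value for each patient, and 3.8.2 does not say what value such a patient receives. If 3.8.1 is applied literally to a duration built from start and stop dates, a patient without a stop date has no value and drops out. Those still on treatment at the cut-off are by construction long-treated, so losing them shortens the summary, and more so for regimens with longer treatment.

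Two things are at stake. First, one report could give two different first-line durations, with the one that ignores censoring carrying the primary label. Second, later lines have only the uncensored method, with no Kaplan-Meier result to set beside it.

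**Working it through.** **1. The plan's own figure.** The only design figure is the precision of regimen proportions in Table 5. With half-width 1.96 × √(p(1−p)/n) and n = 300, p = 5%, 10% and 20% give 2.47%, 3.39% and 4.53%. These match the stated ±2.5%, ±3.4% and ±4.5%. Nothing comparable is given for duration.

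**2. Inputs.**
- Treatment starts run from 1 January 2016 to 31 December 2018 (3.2.2) and observation ends on 31 January 2020 (3.2.3.2). Potential follow-up A therefore runs from a = 13.0 to b = 49.0 months.
- The time scale comes from the retrospective study cited in Section 1, with first-line PFS of 6.4 and 5.4 months in BRAF-mutant disease. Using PFS as a proxy for duration is an assumption.
- Further assumptions: exponential durations with rate λ = ln 2 / median, uniform starts and, to begin with, nobody lost.

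**3. Share still on treatment at cut-off.** p = (e^(−λa) − e^(−λb)) / (λ(b − a)).
- Median 5.4: λ = 0.1284; p = (0.1882 − 0.0019) / (0.1284 × 35.98) = 0.040, or 12 of 300.
- Median 6.4: λ = 0.1083; p = (0.2444 − 0.0050) / (0.1083 × 35.98) = 0.061, or about 18 of 300.

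**4. Effect of dropping them.** Below 13.0 months every duration is fully observed, so the complete-case median is −ln((1 + p)/2)/λ. The complete-case mean is (1/λ − E[A·e^(−λA)] − p/λ)/(1 − p), where E[A·e^(−λA)] is 0.825 and 1.321.

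| Assumed median | Complete-case median | True mean | Complete-case mean |
|---|---|---|---|
| 5.4 | 5.09 (−6%) | 7.79 | 6.93 (−11%) |
| 6.4 | 5.85 (−9%) | 9.23 | 7.83 (−15%) |

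In a simulation of this set-up, Kaplan-Meier on all patients returned the assumed medians to within 0.03 months.

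**5. If the cut-off date served as the stop date.** The mean becomes (1 − p)/λ: 7.48 instead of 7.79 (−4%) and 8.67 instead of 9.23 (−6%). The median does not change, because it lies below 13.0 months.

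**6. Sensitivity (simulated).**
- Loss before an observed end (no rate is given in the documents): 10% lost gives medians 14% and 16% too short; 20% lost gives 22% and 24%.
- Longer durations, nobody lost: an assumed median of 9 months gives 12% ongoing, with the median 17% and the mean 26% too short. A median of 12 months gives 20% ongoing, with 26% and 36%.
- Opposite direction: if 10% die on treatment within 2 months and have no stop date, dropping them lengthens the median, from 4.6 to 5.1 months in the 5.4-month case and from 5.4 to 5.9 in the 6.4-month case.

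**7. Later lines.** The documents give no duration for second or later lines, so no size is attached there. The gap itself is plain: 3.8.4 inherits 3.8.2, and Table 2 and 3.8.3 are confined to first line.

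**The case against.** The strongest reply is that first-line duration is already handled properly elsewhere. Section 2.2 equates treatment duration with time to treatment cessation, 3.3.1 and Table 2 use the same three end events, and Table 2 states a censoring rule. This stands. A reader might infer that Kaplan-Meier is planned only as a graph, or for a different event. The synopsis rules out the first by promising medians, quartiles and CIs. The body text does not support the second; only the synopsis version of the primary endpoint leaves out switch.

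A reader might also infer that the plan decides to exclude ongoing patients and that the primary result is therefore biased short. The documents do not say so. Section 3.8.5 describes missing data as items not collected or documented, which need not cover a patient recorded as still on treatment. Detail is deferred to a SAP due before database lock. A missing drug stop date need not remove a patient either, since progression or switch also ends the interval. Nor is the direction certain, as step 6 shows.

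Finally, the size is modest. With n = 300 the approximate 95% half-width of an exponential median is 1.96/(λ√300), or 0.88 and 1.04 months. The shifts of 0.31 and 0.55 months are about 35% and 53% of that.

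None of this supplies a rule for 3.8.2, and no Kaplan-Meier analysis exists for later lines.

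**Conclusion.** The point holds as a gap in the stated method and is worth correcting. The analysis labelled primary has no censoring rule for duration, sits beside a censored analysis of nearly the same first-line interval, and is the only method for later lines. If ongoing patients were dropped, first-line medians would be about 6-9% and means about 11-15% too short. This rests on exponential durations, uniform starts over 2016-2018, nobody lost to follow-up and PFS of 5.4 to 6.4 months standing in for treatment duration. The figures show what a literal reading would do; they are not a bias the plan has committed to. Loss to follow-up or longer durations would increase them, and early deaths on treatment without a stop date could reverse the sign.

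**What to change.** - **3.8.2:** estimate first-line duration by Kaplan-Meier (median and quartiles with 95% CI), using the Table 2 events and censoring rule for time to treatment cessation. Censor only patients with no progression, discontinuation or switch. Censoring everyone without a drug stop date would wrongly censor patients whose progression is documented.
- **3.8.4:** apply the same method to second and later lines, with the clock starting at that line.
- **Reporting:** give the number censored, with deaths on treatment shown separately because Table 2 censors at death. Present simple descriptive statistics only beside that number.
- **Consistency:** state the median, quartiles and CIs in 3.8.3 to match the synopsis, and align the synopsis primary endpoint with 3.3.1 on switch.

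The cost is wording in the protocol and SAP and minor extra programming, mainly for later lines. No new data item is needed for first line. For later lines, the SAP should confirm that the collected dates identify the same end events.
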